### 8.3 Study Participants

# 8.3.1 Overall Description of Study Participants

Participants in the study will be women aged 18 and above with a lesion of suspicion 3, 4 or 5 following mammography and ultrasound.

### 8.3.2 Inclusion Criteria

To be included in the study the patient must:

- Be willing and able to give written informed consent for participation in the study.
- Be female, aged 18 years or above.

### 8.3.3 Exclusion Criteria

The presence of any of the following will preclude patient inclusion:

- Known or suspected pregnancy
- Breast implant
- Previous breast cancer
- Known renal impairment
- History of anaphylactoid or anaphylactic reaction to any contrast media

- Contrast media within 24 hours prior to CESM
- Commencement of neo-adjavant chemotherapy, hormone treatment, radiotherapy or surgery for this episode

# 8.4 Study Procedures

# Screening and enrolment

Patients who have been identified as suitable for the study will be approached at the routine post-biopsy consultation when their diagnosis and treatment plan is being discussed. At this meeting, patients will be given both written and verbal information about the study.

If a patient wishes to enter the study, their eligibility will be checked by a Research Radiographer or Research Nurse and signed informed consent will be obtained. The patient will then be randomised and if she is in the CESM arm an appointment will be arranged for the procedure.

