## 5.

# STUDY SYNOPSIS **Study Title** An assessment of the impact of **CONT**rast **EN**hance**D** Spectral Mammography (CESM) on patient management and comparison with MRI (CONTEND Study) Internal ref. no. RADIOL/2015/CONTEND **Study Design** The aim of this pilot study is to establish the Contrast Enhanced Spectral Mammography (CESM) technique and study procedures. Results of this pilot and feedback from staff will inform Phase 2 of the study which will be a larger, multi-centre, randomised control trial. The study will be undertaken by members of the Cambridge Breast Unit (CBU) at Addenbrooke's Hospital, Cambridge using CESM technology provided by GE Healthcare as an upgrade to the GE Senographe Essential digital mammography system. This technology is already established throughout the world and has FDA approval and is CE marked. This will be a randomised, sequential cohort study. Following standard mammography and ultrasound all women with lesions of suspicion 3, 4 or 5 will be randomised to either receive CESM in addition to their assessment procedure or to receive usual care. Sealed envelopes will be held at CBU reception desk containing either 'CESM' or 'Usual Care' and one will be selected at random to determine to which arm of the study the woman is allocated. After providing informed consent, those women randomised to receive CESM will undergo the procedure either during the same clinic visit or on a day following the initial clinic visit. This will be dependent upon clinic time and staff availability and the woman's own preferences / circumstances. The index lesion and any additional disease detected by CESM will be biopsied as appropriate and results will be discussed at the multidisciplinary meeting (MDT). For those with biopsy confirmed disease a decision will be made at that meeting regarding conservation surgery, mastectomy or neo-adjuvant therapy. For those with benign disease

confirmed by core biopsy standard care will be followed.

MRI will be performed on appropriate women in line with standard practice. Additional disease detected by MRI will be biopsied if this will influence patient management. Biopsies will be undertaken using either ultrasound or MRI guidance. These cases will be discussed at the MDT and a decision made regarding conservation surgery, mastectomy or neo-adjuvant therapy.

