The pathway for women randomised to receive usual care will be the same as for those randomised to receive CESM, excluding the CESM procedure, i.e. they will undergo biopsy during their initial clinic visit and results will be discussed at the MDT where a decision regarding their future management will be made.

A flowchart illustrating patient pathways during the CONTEND Study can be found in Appendix I of this document.

A proforma will be used for each case to record patient pathway, results of biopsies and MDT patient management decisions.

Staff will be asked to provide feedback on patient acceptability and ease of undertaking the CESM procedure. They will also be asked to record any incidents of note, e.g. patient related problems; impact on clinic; issues with equipment. Time taken to undertake the examination will be recorded.

In order to compare the diagnostic accuracy of CESM with MRI, CESM images and MRI images will be anonymised and read by different readers - CESM images will be reported without the knowledge of the MRI results and vice versa. Mammography and ultrasound images will be available. A completed report on a proforma will be the basis for statistical analysis.

Histopathology data collected following surgery or from core biopsy if surgery is not undertaken and will be used as the gold standard for measurement of tumour size and extent of disease. If the patient is having primary drug therapy, tumour size will be determined from the mammogram.

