# Rationale

Treatment options for women with proven invasive breast cancer depend on the size of the tumour and the presence and location of any additional disease (12). Breast MRI, using MRI specific contrast media, is currently recognised as the most sensitive imaging technique in determining the extent of disease identified on mammogram or by ultrasound. This means the patient can go straight to definitive surgery rather than having surgical under treatment, i.e. the identification of additional disease may mean the woman has a mastectomy rather than a wide local excision (lumpectomy).

There are several disadvantages of MRI. It is usually performed in a different department from mammography and ultrasound, which can pose problems with accessibility and may delay patient care. Image acquisition takes an average of 40 minutes and the whole procedure can take up to 90 minutes. MRI is also known to produce a higher frequency of false positives than conventional mammography and this can lead to unnecessary surgery and patient anxiety. Some patients may be excluded from undergoing MRI due to claustrophobia or presence of metal within their body. In the UK, MRI is currently used selectively, based on NICE guidelines (13). There are also economic considerations - MRI is expensive.

CESM is being heralded as a diagnostically comparable, less labour-intensive and cost effective technique to breast MRI. Like MRI, CESM can be used to identify lesions not seen on mammography or ultrasound and to assess the size of lesions and stage of disease. The procedure can be performed on the same day using the same equipment and in the same department as a woman's initial clinic visit. This should reduce patient anxiety and has the potential of a definitive decision on patient management being made earlier in the patient pathway. CESM also has the potential to be used as a screening tool in certain groups of women which is not clinically viable with MRI.

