#### 7. **OBJECTIVES**

### 7.1 **Primary objective**

To assess the impact the addition of CESM has on patient management. The hypothesis is that CESM should afford a definitive management decision earlier in the patient pathway.

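### The protocol gives two incompatible enrolment sequences, no endpoint for its earlier-decision hypothesis, and a rule that removes randomised women from the CESM arm

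*Protocol*

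**What the plan says.** **Sequence.** Section 5 (synopsis) states: "Following standard mammography and ultrasound all women with lesions of suspicion 3, 4 or 5 will be randomised". Consent is mentioned after that. CESM may be done at the same visit or on a later day, and biopsy of the index lesion and of any extra disease seen on CESM comes next. Of usual-care women it says "they will undergo biopsy during their initial clinic visit and results will be discussed at the MDT". Section 8.4, under Screening and enrolment, has suitable women "approached at the routine post-biopsy consultation when their diagnosis and treatment plan is being discussed"; eligibility check, consent, randomisation and a CESM appointment then follow in that order. Section 8.1, under Trial duration, also places recruitment after the results consultation.

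**Hypothesis and endpoint.** Section 7.1 hypothesises that "CESM should afford a definitive management decision earlier in the patient pathway". The Rationale says of CESM, "The procedure can be performed on the same day using the same equipment and in the same department", meaning those of the woman's first clinic visit, and adds that this "has the potential of a definitive decision on patient management being made earlier in the patient pathway". The primary endpoint, in the synopsis and in Section 8.2, is the finding of additional disease that alters management. The secondary endpoints concern accuracy, lesion size, additional lesions and false positives.

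**Data recorded.** The synopsis says: "A proforma will be used for each case to record patient pathway, results of biopsies and MDT patient management decisions". The one duration it names is that of the examination: "Time taken to undertake the examination will be recorded".

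**Withdrawal.** Section 8.1, under Subject withdrawal criteria, withdraws anyone who has ill-effects from the contrast or the procedure, or cannot complete it for any reason. It excludes from analysis the data of these women and of those who choose to leave.

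**The concern.** The pilot is meant to establish study procedures, to examine the effect of CESM on management decisions and to inform a larger randomised trial. The point of randomisation determines whether the diagnosis is already known at entry, whether CESM can affect the biopsy or the first treatment plan, and what a change in management is measured against. If staff work from different sections, the trial has no single definition of the intervention's place in the pathway, and no analysis can restore one afterwards.

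A hypothesis about an earlier decision needs an outcome that can show it. Finding extra disease that changes the plan is a different quantity: CESM could alter many plans without speeding any, or speed many without altering them.

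Dropping women after randomisation because of something that happens only in one arm also breaks the comparability that randomisation provides. Women who react to contrast or whose procedure is not performed may differ from completers in ways related to management, and usual care has no matching removal.

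**Working it through.** **1. The two sequences side by side.**

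| Step | Section 5 | Sections 8.1 and 8.4 |
|---|---|---|
| Point of entry | After mammography and ultrasound | At or after the post-biopsy results consultation |
| Biopsy | Follows randomisation | Already done |
| Consent | Mentioned after randomisation | Before randomisation |
| CESM | Same visit or a later day | By appointment after randomisation |
| Treatment plan at entry | Not yet made | Under discussion |

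Biopsy cannot both follow randomisation and precede it. Section 11.1 requires consent before any study-specific activity, so the consent order in the synopsis also needs clarifying.

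**2. What CESM can influence.** The Rationale links the earlier decision to CESM being possible on the day of the first clinic visit. The synopsis allows that. The Section 8.4 sequence does not: by the time of randomisation the plan is being discussed, so CESM can precede only a later decision, for example one that awaits MRI.

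**3. Hypothesis against endpoints.** None of the endpoints in the synopsis or Section 8.2 contains a time or a pathway stage. The proforma records pathway and MDT decisions for each case, so a source exists, but no endpoint draws on it.

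**4. One-sided removal.** The plan's own count is reproduced first: 50 CESM examinations / 0.5 allocated = 100 women, which holds only if no CESM examination fails.

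Let N be the women allocated to CESM, d the proportion removed and x the number of completers with a management change. Over all allocated women the proportion lies between x/N (no removed woman had a change) and (x + dN)/N (all did). The width is d. The protocol gives no value of d, so 5-20% is an assumption:

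| d | Removed if N = 50 | Width of bounds |
|---|---|---|
| 5% | 2.5, about 3 | 5 points |
| 10% | 5 | 10 points |
| 20% | 10 | 20 points |

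Example: 5 of 50 are removed and 9 of the 45 completers (20%) have a change. The proportion for all allocated women lies between 9/50 = 18% and (9 + 5)/50 = 28%.

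If recruitment instead continues until 50 examinations succeed, N = 50/(1 - d): 50/0.95 = 52.6 (about 53) to 50/0.80 = 62.5 (about 63). Removals are then about 3 to 13. The width is still d.

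These bounds are extremes. For a milder case, suppose the true rate is 20% in both arms and 10% of the CESM arm is removed. The observed CESM rate is (0.20 - 0.10 × 0)/0.90 = 22.2% if none of those removed had a change, and (0.20 - 0.10 × 0.40)/0.90 = 17.8% if 40% of them did. The bias is about 2.2 points either way. With 20% removed the rates are 25% and 15%, a bias of 5 points either way.

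**The case against.** This is a pilot with no power calculation and no stated between-arm test, so bias in an arm comparison matters less than in a confirmatory trial. That is fair, but establishing procedures and learning how CESM affects management are its stated purposes, and an unsettled entry point undermines both. Appendix I has a flowchart that is not available here; whatever it shows, the two texts still disagree.

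A reader might infer that the timing hypothesis cannot be tested at all. The documents do not support that. Earlier in the pathway can mean an earlier stage, such as before MRI, as well as an earlier date. The stated analysis covers actual or hypothetical decisions, and the proforma holds the raw material. What stands is that no endpoint is named for it.

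A reader might infer from Section 10.2, which limits the analyses to women with MRI, CESM and surgical pathology data, that every usual-care woman is excluded. Every method in that section concerns CESM against MRI or histopathology, and Section 8.4 describes the management analysis separately. This is a scope to clarify, and no loss should be attached to it.

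A reader might blame the contradiction for any mixture of CESM before and after biopsy. The synopsis alone could produce one, since it allows CESM on a later day while biopsy belongs to the first visit.

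On withdrawals, women who choose to leave can do so in either arm, and known renal impairment is already an exclusion, which limits losses at the creatinine check. Non-completion and ill-effects of CESM still arise in one arm only.

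**Conclusion.** Three points hold. First, the enrolment sequences in Section 5 and in Sections 8.1 and 8.4 cannot both be followed, and the choice determines which decision CESM can influence. Second, the Section 7.1 hypothesis has no matching endpoint, although the data source for one exists. Third, the Section 8.1 withdrawal rule removes randomised women from the CESM arm with no counterpart in usual care, so a comparison of management by arm can be biased in either direction.

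The first two points rest on the text alone and carry no figure. The size of the third depends on a non-completion rate that the protocol does not give; at an assumed 5-20%, the worst-case bounds are 5-20 percentage points wide.

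The documents do not show which sequence is intended. The synopsis is the outlier against Sections 8.1 and 8.4, but its order fits the Rationale better. Two matters are clarifications only: the scope of Section 10.2, and the words *by CESM*, which appear in the synopsis endpoint but not in Section 8.2. With those words, usual care could not record an event.

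**What to change.** 1. The sponsor should reconcile Sections 5, 8.1 and 8.4 and the Appendix I flowchart into one order of consent, randomisation, CESM and biopsy, and state which management decision CESM is meant to influence under it. Either order has a price: entry before biopsy enrols women whose diagnosis is unknown, and entry after it leaves CESM only later decisions to affect. The choice is the sponsor's.
2. Either name an outcome for time, or pathway stage, to the definitive management decision, taken from the MDT entry on the proforma in both arms, or reword the Section 7.1 hypothesis to match the existing endpoint. If the outcome is added, state that it is collected even though Section 8.1 ends participation once CESM is done.
3. Compare management outcomes by allocated arm in all randomised women. Keep the data of those who cannot complete CESM unless they withdraw consent to its use, and amend the withdrawal text in Section 8.1 to match.
4. Use one arm-neutral endpoint wording for the between-arm comparison, report disease found by CESM as a descriptive yield in the CESM arm, and state that the Section 10.2 population applies only to the CESM-versus-MRI accuracy analyses.

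The cost is a protocol amendment with sponsor agreement and REC approval (Sections 11.2 and 11.3) and a few dates added to a proforma already completed for each case.

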# **CESM** procedure

Patients will be given an intravenous injection (via a power injector), into their arm, of an iodine based contrast media. This type of contrast media is used routinely in CT imaging procedures and the Cambridge University Hospitals NHS Trust Patient Group Directive for its administration will be adhered to. Patients will be asked to complete the Patient Contrast Questionnaire prior to the procedure (see Appendix II) and have their creatinine level checked using a Point of Care (PoC) device in the CT department. If serum creatinine is elevated >150 mmol/l the procedure will not be performed.

Two minutes after the injection, two mammographic exposures will be taken automatically, within approximately one second of each other, in each of the standard mammographic views (RCC, RMLO, LCC, LMLO).

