# 9. SAFETY REPORTING

### 9.1 Definition of Serious Adverse Events

A serious adverse event is any untoward medical occurrence that:

- Results in death,
- · Is life-threatening,

- Requires inpatient hospitalisation or prolongation of existing hospitalisation,
- Results in persistent or significant disability/incapacity, or
- Is a congenital anomaly/birth defect.
- Other important medical events\*

\*Other events that may not result in death, are not life threatening, or do not require hospitalisation, may be considered a serious adverse event when, based upon appropriate medical judgement, the event may jeopardise the participant and may require medical or surgical intervention to prevent one of the outcomes listed above.

After injection into an artery or vein, it is uncommon (1% risk = 1-10 in 1,0000) to experience pain and discomfort

Rare effects (0.1% risk=1-10 in 10,000) include diarrhoea, irregular heartbeat, kidney problems, cough, fever, general discomfort or dizziness

Very rare (0.01%=less than1in 10,000) include seizures (fits), clouding consciousness, disturbance of senses like touch, trembling, flushing, difficulty breathing including severe breathing difficulty due to fluid in the lungs, short term brain disorders (encephalopathy), short term memory loss, coma and stupor or myocardial infarction.

Any allergic or anaphylactic reactions to the contrast media used in CESM are likely to occur soon after the injection. These will be managed according to local policies by members of the breast team. Minor reactions, e.g., skin rashes, hives (urticaria), itching (pruritus), nausea, dizziness, runny nose (rhinorrhea), brief retching and /or vomiting will be monitored until symptoms have alleviated or further action is needed.

Moderate reactions, e.g. headache, persistent vomiting, wheezing (mild bronchospasm), palpitations, facial swelling, raised blood pressure (hypertension), abdominal cramps; may require an injection of antihistamine and/or adrenaline. An emergency drugs pack will be available in the room during CESM procedures for this purpose.

In the exceptional event of a serious reaction which has the potential to be life-threatening, e.g. difficulty breathing (overt bronchospasm), chest pain, irregular heartbeat (arrhythmia), collapse, seizure, cardiac arrest; a 'crash' call will be made to summon the emergency medical team.

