# **CONTEND** study

# Patient contrast questionnaire

Affix	patient	ΙD	label	here
	patient	ייו	label	11010

As part of the Contrast Enhanced Spectral Mammography (CESM) procedure, we are seeking your permission to administer an injection of contrast medium (dye) as part of your examination.

We need to ask you the following questions prior to your injection:		
Have you had injections of contrast medium in any past examinations in x-ray?	Yes	No
If yes, did you have any problems related to this injection?	Yes	No
If yes, please state:	1	
Are you allergic to anything?	Yes	No
If yes, please state:		
Do you have asthma?	Yes	No
Are you diabetic?	Yes	No
If you are diabetic, do you take metformin?	Yes	No
Do you have an overactive thyroid? (hyperthyroidism)	Yes	No
Are you on interleukin 2 therapy?	Yes	No
Do you suffer from sickle cell anaemia?	Yes	No
Do you suffer from Chronic Kidney Disease (CKD)?	Yes	No

Do you suffer from any brain pathology? Tumour, epilepsy, seizures?				Yes	No
If yes, are you currently taking any	med	ication for this? Ple	ease state:	Yes	No
Please state the date of the first da	ay of y	your last menstrua	I period:		
Please state the date of the first da	ay of y	your last menstrua	<del>l period:</del>		
Is there any chance you might be p	oregn	ant?		Yes	No
Do you use oral contraceptive pill?				Yes	No
Do you take hormone replacement	thera	apy (HRT)?		Yes	No
Please do not sign this form unt	il you	ı are with the rad	iographer.		
Print name		Signature		Date	
For official use only					
Date of blood test: eGF		R: Serum creatinine:			
Practitioner		Signature		Date	

CONTEND Study	Version number: 4.0	Version date: 24.0216

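### The creatinine stop rule in section 8.4 is written in mmol/l, 1,000 times the evidently intended limit in micromol/l

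*Protocol*

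**What the plan says.** Section 8.4 of the protocol (CESM procedure) gives an iodine-based contrast agent intravenously by power injector. Before the injection, women complete a contrast questionnaire and "have their creatinine level checked using a Point of Care (PoC) device in the CT department". The rule for acting on the result follows: "If serum creatinine is elevated >150 mmol/l the procedure will not be performed".

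Other parts of the protocol that bear on renal safety:

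- Section 8.3.3 excludes women with "Known renal impairment" and gives no laboratory value.
- Section 9.1 names renal effects of the contrast agent: "Rare effects (0.1% risk=1-10 in 10,000) include diarrhoea, irregular heartbeat, kidney problems".
- Appendix II asks about chronic kidney disease. It has official-use fields for eGFR and for "Serum creatinine", with no unit or limit beside either.
- Section 8.4 also refers to a local rule: "Cambridge University Hospitals NHS Trust Patient Group Directive for its administration will be adhered to". The content of that directive is not reproduced.

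**The concern.** A limit of 150 is familiar for serum creatinine in micromol/l. In mmol/l it lies far outside anything that can be measured in a living patient. As this is the only numeric renal threshold in the protocol, a reader cannot recover the right unit from another section.

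The exclusion criterion and the kidney disease question mainly catch impairment that is already known. The point-of-care measurement is the step that can find impairment nobody knew about, in women about to receive contrast as a research procedure. A stop rule that cannot be met leaves that step with no written consequence.

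**Working it through.** **Inputs**

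- Limit as written: 150 mmol/l (section 8.4).
- Molar mass of creatinine: 113.12 g/mol. This is a chemical constant and is not in the protocol.
- 1 mmol/l = 1,000 micromol/l.

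The protocol derives the limit from nothing, so there is no calculation of its own to reproduce. The check is a unit conversion.

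**Step 1: the limit as written.** Mass concentration = molar concentration × molar mass.

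0.150 mol/l × 113.12 g/mol = 16.97 g/l. Multiplying by 1,000 (g to mg) and dividing by 10 (l to dl) gives about 1,697 mg/dl.

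**Step 2: the same number in micromol/l.**

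0.000150 mol/l × 113.12 g/mol = 0.01697 g/l, or about 1.70 mg/dl.

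**Step 3: ratio.** 0.150 / 0.000150 = 1,000.

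**Step 4: could the written rule ever trigger?** Possible readings, converted to mmol/l and compared with the limit of 150:

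| Reading (micromol/l) | In mmol/l | Above 150 mmol/l? |
|---|---|---|
| 60 | 0.06 | No |
| 100 | 0.10 | No |
| 150 | 0.15 | No |
| 500 | 0.50 | No |
| 1,000 | 1.0 | No |
| 2,000 | 2.0 | No |

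The last row is an assumed extreme. Even there the reading is 2/150 = 1/75 of the written limit.

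**Step 5: is it corrected elsewhere?** Section 8.3.3 has no number. Section 9.1 names kidney effects without a threshold. The Appendix II fields carry neither unit nor cut-off. The Patient Group Directive may contain a correct limit, but the protocol does not show it. No section restates the rule in another unit.

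**The case against.** The strongest objection is that the finding turns on one character. A micro sign in a symbol font can be read from a PDF as a plain m, and that would not be the sponsor's error. Clean text around the sentence is weak evidence against this, because that paragraph contains no other special symbol that could have been misread, and the extracted text of Appendix II does show garbled characters. This stands as a limit on confidence. It does not settle the matter the other way, since a typed mmol/l is an ordinary drafting slip and is what the available text says.

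The second objection is that little would go wrong in practice. Staff would probably compare a reading in micromol/l with 150 and stop where they should. The known-impairment exclusion, the kidney disease question, the eGFR field and the directive all remain in place. This also stands, and it rules out any claim that patients were exposed to harm. It does not rescue the sentence. The eGFR field has no action limit attached, the directive's limit cannot be seen, and the protocol sets its own limit beside the directive. Section 14 forbids planned departures from the protocol, so a safety rule should work as written and not depend on readers correcting it silently.

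Finally, the slip is a unit label and has no statistical consequence. That is agreed. It is raised because the sentence decides whether a participant receives contrast.

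**Conclusion.** The concern holds. The stop rule as written is 1,000 times the evident intent (about 1,697 mg/dl against about 1.70 mg/dl) and could never be met. It should be fixed because it is a participant-safety threshold, although actual harm is unlikely and nothing in the design, sample size, endpoints or analysis depends on it.

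The conclusion rests on two assumptions. The first is that the source page prints mmol/l as the extracted text does. The second is that micromol/l was intended, which the protocol never states but which is the only plausible reading of 150. Confidence that the error is the sponsor's is therefore medium; the conversion itself is not in doubt.

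**What to change.** Check the source page of section 8.4 for a micro sign. If it is there, no change is needed. If the page prints mmol/l:

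1. Change the unit to micromol/l, spelled out or otherwise protected against loss of the symbol.
2. Confirm the value 150 against the Trust's Patient Group Directive and against the unit the point-of-care device reports.
3. Optionally, print the unit beside the creatinine field in Appendix II.

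The cost is a one-line correction to section 8.4, with no effect on design, sample size or analysis.
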